8. ORGANISATION AND RESPONSIBILITIES

The Chief Investigator is responsible for the management, central co-ordination of clinical and administrative aspects of the study, compliance with the Research Governance Framework and management of study budget. Relevant ethics committee and Trust research governance approval will be coordinated centrally for efficiency and speed.

All investigators are responsible for ensuring that the research they undertake follows the agreed protocol, for helping care professionals to ensure that participants receive appropriate care while involved in research, for protecting the integrity and confidentiality of clinical and other records and data generated by the research, and for reporting any failures in these respects, adverse reactions and other events or suspected misconduct through the appropriate systems.

8.1. Centre eligibility

Initially, six hospitals in six NHS Trusts will recruit women into the study. These centres will receive equipment for the PO test from the study and will be funded to employ a part-time research midwife to conduct the study. Other centres wishing to participate can do so provided their Trust will supply the above resources.

8.2. Local Co-ordinator at each centre

Each Trust has a designated Consultant Neonatologist to act as Principal Investigator and bear responsibility for the conduct of research at their centre. Close collaboration between

^{*} Appropriate criteria of proof beyond reasonable doubt cannot be specified precisely, but a difference of at least three standard deviations in an interim analysis of a major endpoint may be needed to justify halting, or modifying, the study prematurely. If this criterion were to be adopted, it would have the practical advantage that the exact number of interim analyses would be of little importance, so no fixed schedule is proposed.

midwifery and clinical teams is particularly important in order to ensure that recruitment of babies is maximised. The responsibilities of the Principal Investigators will be to ensure that all medical and post-natal ward staff involved are well informed about the study. This will involve distributing protocols and patient information sheets to all relevant staff, displaying publicity material where it is likely to be read, and contributing to the regular newsletters. The Principal Investigators should liaise with the study administrator on logistic, data collection and administrative matters connected with the study.

8.3. Midwifery Co-ordinator at each centre

Each participating centre will have a designated research midwife who will act as Local Midwifery Coordinator. This person would be responsible for ensuring that all eligible babies are considered for the study, that patients are provided with study information sheets, and have an opportunity to discuss the study if required. The midwife will be responsible for the organisation of data collection and will be the first point of contact for data queries.

8.4. The Study Office

The Study Office at the University of Birmingham Clinical Trials Unit (BCTU) is responsible for providing all study materials, including the coded stickers and questionnaires. Additional supplies of any printed material can be obtained on request. The Study Office is also responsible for collection and checking of data (including reports of serious adverse events) and for analyses. The Study Office will help resolve any local problems that may be encountered in study participation.

8.5. Research Governance

The conduct of the study will be according to the principles of MRC Guidelines for Good Clinical Practice in Clinical Trials (1998) and the appropriate NHS Research Governance Frameworks.

All centres will be required to sign an Investigator's Agreement, detailing their commitment to accrual, compliance, Good Clinical Practice, confidentiality and publication. Deviations from the agreement will be monitored and the SSC will decide whether any action needs to be taken, e.g. withdrawal of funding, suspension of centre.

The Study Office will ensure researchers not employed by an NHS organisation who interact with individuals in a way that has direct bearing on the quality of their care hold an NHS honorary contract for that organisation.

8.6. Regulatory and Ethical Approval

Site specific approval from local research ethics committees (LREC) will be gained for each site following Multi-centre Research Ethics Committee (MREC) approval. The LREC and Trust Research and Development Office will assess each site for "locality issues" relating to their population, the investigators, the facilities and resources.

8.7. Funding and Cost implications

The research costs of the study are funded by a grant from the NHS R&D Health Technology Assessment Unit awarded to the University of Birmingham.

The study has been designed to minimise extra 'service support' costs for participating hospitals, with no extra visits to hospital and no extra tests. Additional costs associated with the study should be minimal. These costs should be met by accessing the Trust's budget.

8.8. Indemnity

There are no special arrangements for compensation for non-negligent harm suffered by patients as a result of participating in the study. The study is not an industry-sponsored

study and so ABPI/ABHI guidelines on indemnity do not apply. The normal NHS indemnity liability arrangements for research detailed in HSG96(48) will operate in this case.

However, it should be stressed that in terms of negligent liability, NHS Trust hospitals have a duty of care to a patient being treated within their hospital, whether or not that patient is participating in a clinical study. Apart from defective products, legal liability does not arise where there is non-negligent harm. NHS Trusts may not offer advance indemnities or take out commercial insurance for non-negligent harm.

8.9. Publication

A meeting will be held after the end of the study to allow discussion of the main results among the collaborators prior to publication. The success of the study depends entirely on the wholehearted collaboration of a large number of doctors, midwives and others. For this reason, chief credit for the main results will be given not to the committees or central organisers but to all those who have collaborated in the study. Collaborators will be permitted to publish data obtained from participants in the Pulse Ox Study that use study outcome measures but do not relate to the study objectives.

APPENDIX C: SERIOUS ADVERSE EVENT FORM

Please report any **serious, unexpected** adverse events² believed to be due to the treatments given as part of the Pulse Ox study by sending or faxing the following details to the Pulse Ox Study Office ([contact]) within 2 weeks of the event:

Patient's Full Name:

Date of Birth: Hospital Number:

Responsible doctor:

Date Treatment Started:(if known).....

Date Event Started:..... Date Event Ceased:

Outcome (e.g. fatal, recovered, continuing):.....

Details of Adverse Event (please attach copies of relevant reports).....

.....
.....
.....

Did the event require or prolong hospitalisation?

Please give reasons why you consider the event to be treatment-related:

.....
.....

Name of Person Reporting (please print).....

Telephone Number:..... Today's Date:

² For the purposes of this study, "**serious**" adverse events are those which are fatal, life-threatening, disabling or require hospitalisation. "**Unexpected**" adverse experiences are defined as those that would not be expected as a result of PO testing. It is not required to report in this way side-effects or events that might reasonably be expected.

APPENDIX D: PULSE OX STUDY DATA COLLECTION FORM

Section 1: Eligibility

Is the baby well? Yes No

If the baby is **well**, they are **eligible** for the study. Please ensure consent has been taken and continue with **sections 2 – 5 below**.

If the baby is **not well**, they are **not eligible** for the study. Please complete the '**Ineligibility Form**', put in the participant pack and put it in the Pulse Ox collection box. Treat the baby as normal.

Section 2: Identifying Details

Baby Hospital Number

Baby **NHS** number

Baby date of birth ____ / ____ / ____

Time (24hr) ____ : ____

Male Female

Gestational age ____ /40 weeks

Mother's Forename _____

Mother's Surname _____

Hospital Number

Mother's NHS Number

Mother's date of birth ____ / ____ / ____

(or attach sticker)

Mother's gravida ____ parity ____

Section 3: Language

Was a translator and/or a translated version of the Information Sheet and Consent required? Yes No

If yes, specify language: _____

Section 4: Pulse Oximetry Saturations

First reading (This should be taken within 24 hours of age or before discharge)

Performed in: Delivery Suite Post Natal Unit Neonatal Unit

Performed by:

PRINT NAME: _____

Doctor Nurse Midwife Midwifery Assistant Care Assistant Neonatal nurse

Date	Time	Foot sats (%)	Right hand sats (%)	% difference	Pass/Refer

If the result is normal (i.e. **Pass**), nothing further needs to be done. Please **ensure sections 1-5 are completed**. Please put this form in the participant pack and put it in the Pulse Ox collection box.

If less than 95% in either limb or $\geq 3\%$ difference between limbs, this is a **Refer**, the baby needs to be examined/ reviewed by someone trained in neonatal examination. **Please continue with section 6 overleaf**.

Section 5: Antenatal Diagnosis

Is there a family history of congenital heart defects? Yes No

Was CHD suspected on antenatal ultrasound? Yes No

The following sections only need to be completed if the first pulse oximetry reading was <95% in either limb or ≥3% difference between limbs i.e. a **Refer**.

Section 6: Clinical Examination

Undertaken by: Nurse/ Midwife SHO/ Registrar Consultant Other

How long did the exam take? _____ minutes

Did the baby show signs of CHD at examination? Yes No

If yes, was this murmur cyanosis abnormal pulses

Overall exam finding Normal Abnormal Details: _____

If exam is normal, a second PO reading needs to be taken. This should be taken 1-2 hours after the first reading. Please complete section 7 below.

If exam is abnormal, the baby needs to be referred straight to the Neonatal team for further investigation and management. A second PO reading does not need to be taken. Please continue with sections 9-14 overleaf.

Section 7: Second Pulse Oximetry Reading

Performed in: Delivery Suite Post Natal Unit Neonatal Unit

Performed by:
PRINT NAME: _____

Doctor Nurse Midwife Midwifery Assistant Care Assistant Neonatal nurse

Date	Time	Foot sats (%)	Right hand sats (%)	% difference	Pass/Refer

*If less than 95% in either limb or ≥3% difference between limbs, this is a **Fail**, the baby needs to be referred to the Neonatal team for further investigation and management. Please continue with sections 8-14 overleaf.*

*If the result is normal (i.e. **Pass**), nothing further needs to be done. Please ensure all above sections are completed. Please put this form in the participant pack and put it in the Pulse Ox collection box.*

The following sections only need to be completed if the clinical examination found an abnormality or if the second pulse oximetry reading was a Fail and the baby has been referred to the Neonatal team for further investigation and management.

Section 8: Hyperoxia Test (only to be completed if second PO reading was a fail)

Performed by: Nurse SHO Registrar Consultant

Did saturation increase to 95% or above? Yes No

Section 9: Clinical Symptoms

If baby showed signs of CHD at birth, describe

Collapse Cyanosis Acidosis Respiratory distress

Did this baby have a respiratory illness or any illness other than CHD?

Yes No If yes details: _____

Section 10: Echocardiography

Date of echocardiography ___ / ___ / ___ Time ___ : ___ (24 Hour)

Echocardiographer: Cardiology Research Fellow Other Echocardiographer

Result: Normal Abnormal Uncertain

Details: _____

Section 11: Review of Echocardiography

Reviewed by: Cardiology Research Fellow Consultant Other

(Please tick more than one box if applicable)

Date of review ___ / ___ / ___

Result: Normal Abnormal Uncertain

Details: _____

If there is a *disagreement between the two results* or the result of the review is uncertain, a second echocardiogram needs to be performed. This will be done by a Consultant Paediatric Cardiologist at Birmingham Children's Hospital

Date of second echocardiography ___ / ___ / ___

Result: Normal Abnormal Details: _____

Please continue with sections 12-14 overleaf.

Section 12: Admission Summary

Number of days on Postnatal unit? _____ days

Number of days on Neonatal unit? _____ days

Section 13: Discharge Details

Home Cardiac Unit Other Details: _____

If home, date of discharge ____ / ____ / ____ Time of discharge (24hr) ____ : ____

If cardiac unit, number of days on unit _____ days

Section 14: Death Details

Death Date of death ____ / ____ / ____ Time of death (24hr) ____ : ____

Cause of Death: Cardiac Non-cardiac

If cardiac: Post-operative Other If other, please specify: _____

If non-cardiac, please specify: _____

PULSE OX STUDY
CONGENITAL HEART DEFECT CASE REPORT FORM

Date of Diagnosis ____ / ____ / ____

How was the CHD detected and confirmed?

- Pulse oximetry at birth then echocardiogram
- Clinical examination at birth then echocardiogram
- Post-mortem
- Later echocardiogram by paed cardiologist
- Congenital anomaly registry

Type of CHD?

- Aortic (valve) stenosis Persistent (patent) ductus arteriosus
- Atrial septal defect Tetralogy of Fallot
- Coarctation of aorta Total anomalous pulmonary venous connection
- Complete artioventricular septic defect Transposition of great arteries
- Hypoplastic left heart syndrome Ventricular septal defect
- Interruption of aortic arch

Other (specify) _____

Has the baby had cardiac surgery? Yes No Planned

If yes, when was the surgery ____ / ____ / ____

Type of surgery? _____

Death Date of death ____ / ____ / ____ Time of death (24hr) ____ : ____

Cause of Death: Cardiac Non-cardiac

If cardiac: Post-operative Other

If non-cardiac, please specify: _____

APPENDIX E: DEFINITIONS OF ECHOCARDIOGRAPHIC FINDINGS

Normal	No echocardiographic abnormalities
Non- Significant	No clinical signs (e.g. murmur, thrill, pulse abnormalities, hepatic enlargement) No symptoms Small patent ductus arteriosis (PDA) or small inter-atrial communication (patent foramen ovale (PFO), atrial septal defect (ASD) or muscular ventricular septal defect (VSD)) Mildly abnormal turbulence at branch Pulmonary Artery Echocardiographic findings no longer detected at 6 months
Significant	Small patent ductus arteriosis (PDA) or patent foramen ovale (PFO) or muscular ventricular septal defect (VSD) Mildly abnormal turbulence at branch Pulmonary Artery Above where echocardiographic findings persist for longer than 6 months of age Any cardiac lesion which requires regular monitoring beyond 6 months or drug treatment but does not fall into serious or critical category.
Serious	Any cardiac lesion not defined as critical which requires intervention (cardiac catheterisation or surgery) within 1 year of age
Critical	All infants with hypoplastic left heart, pulmonary atresia with intact ventricular septum, simple transposition of the great arteries or interruption of the aortic arch and all infants dying or requiring surgery within the first 28 days of life with the following conditions: coarctation of the aorta, aortic valve stenosis, pulmonary valve stenosis, tetralogy of Fallot, pulmonary atresia with ventricular septal defect, or total anomalous pulmonary venous connection.

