1.3. Objectives of the Pulse Ox Study

The objectives of the study have been framed to assess PO for screening for CHD in newborn babies in a hierarchical fashion, based on methodologically robust frameworks for evaluation of diagnostic tests outlined by Guyatt *et al* (17) and Fryback and Thornbury (18), as follows.

- To develop PO as a feasible screening tool for CHD in newborn babies.
- To determine the accuracy (sensitivity, specificity, predictive values, and likelihood ratios) of PO for diagnosing critical and serious CHD in newborns, using echocardiography / clinical follow up / congenital malformation registries' data as reference standards (see Appendix E for CHD definitions).
- To determine the psychosocial effect of PO as a screening method among parents and acceptability to health professionals.
- To compare the cost and cost effectiveness of PO and other screening tests (routine neonatal clinical examination and antenatal screening) for improving outcomes of CHD in the newborn using model based economic evaluation.

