2. STUDY DESIGN

2.1. Brief summary

The current neonatal screening for CHD involves a clinical examination undertaken either by a trained health professional prior to discharge from hospital, or by a GP up to 10 days following delivery. The study will evaluate screening using PO undertaken by a midwife within 24 hours of birth. The primary analysis will be accuracy of PO in detecting life-threatening CHD. A comparison of the performance of PO either against, or in addition to, antenatal screening will be made by multivariable logistic regression analysis; another with postnatal clinical examination will be made by decision analytic modelling. The study will also assess parental perception and acceptability to healthcare staff. A cost-effectiveness analysis comparing different screening strategies will be undertaken, using direct study data where possible, in a model-based economic evaluation.

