The participating centres have agreed to make it standard practice to perform PO within each unit and the clinical protocols changed accordingly. PO will be performed before 24 hours or discharge, preferably at around 3-6 hours of age which corresponds to admission to the postnatal ward. PO is routinely performed on babies on the Neonatal Unit. It is painless, extremely well tolerated by babies and requires minimal clinical training. It is estimated that to perform saturations on one hand and one foot will take no more than five minutes. The results of the PO will be recorded as percentage functional saturation for each limb. The date and time of testing will also be recorded. A cut off of <95% in either limb or a difference of $\geq 3\%$ between the limb readings will be considered to be abnormal. This threshold has been shown in previous studies to have the highest sensitivity. It also has the potential to detect coarctation of aorta, a treatable condition that has been missed in earlier studies with different thresholds (14,15) It is anticipated that the maximal sensitivity of the test is achieved by about 6-12 hours of age (9;14;15), by which time we anticipate the majority of babies in this study will have been screened. If PO is low and the clinical examination is unremarkable, the PO will be repeated 1-2 hours later for a definitive definition of abnormality. If the saturations remain low, oxygen will be administered (nitrogen washout or hyperoxia test) to identify potential respiratory causes for low saturations. An echocardiogram will be performed in all case of persisting low saturations (i.e. test positive cases)

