* For the purposes of this study, "serious" adverse events are those occurring in either subjects or testers which are fatal, life-threatening, disabling or require some form of medical or surgical treatment.

difficulties in interpretation as the focus will be only on clinically significant CHD which is likely to be detected equally well by both reference standards.

One of the conclusions that arose from the recent systematic review is the need for a large well conducted study, aimed at improving the precision of the sensitivity estimate of the test. The sensitivity of PO as a screening test for CHD varied between 25% (95% CI, 13% to 41%) (12) and 98.5% (95% CI, 91.8% to 100%) (15) in previously conducted studies. The performance of the test, particularly estimates of sensitivity depends on the absolute number of patients with disease. Thus there is imprecision of the sensitivity estimates due to the low prevalence of CHD in relatively small studies. This study has been planned to be large enough to achieve good precision, as shown in section 6.1.

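### For six lesions, critical status depends on death or surgery by day 28, which the PO result can influence, so critical-only sensitivity may be biased in either direction; the surgery and catheter wording also needs reconciling

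*Protocol*

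**What the plan says.** Appendix E makes four lesions *critical* on anatomy alone. Six others (coarctation, aortic and pulmonary valve stenosis, Fallot, pulmonary atresia with VSD, TAPVC) enter the class only for "all infants dying or requiring surgery within the first 28 days of life with the following conditions". The *serious* class then takes "Any cardiac lesion not defined as critical which requires intervention (cardiac catheterisation or surgery) within 1 year of age".

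The PO result is known to staff and directs what follows. Section 2.2 accepts that the clinical examination cannot be independent of it. Section 4.1 sends every persistently positive baby to echocardiography. After a pass, the form in Appendix D says "nothing further needs to be done", although the routine newborn examination of section 4.2 still takes place. Section 5.5.1 expects that PO may bring to surgery some babies who would otherwise have died first. Section 2.3 seeks cases up to one year.

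On the target condition, section 1.3 speaks of the accuracy "of PO for diagnosing critical and serious CHD in newborns". Section 2.1 says "The primary analysis will be accuracy of PO in detecting life-threatening CHD", a term that Appendix E does not define.

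On recording, the CHD case form in Appendix D asks "Has the baby had cardiac surgery", answered yes, no or planned, with a date if yes. It has no catheter item.

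**The concern.** Take two babies with the same listed lesion. One is detected by PO and needs surgery within 28 days: a critical true positive. The other passes PO, presents later and first needs surgery after day 28. The one-year follow-up finds this baby, but the class is then serious, so the baby leaves the critical denominator instead of counting there as a false negative. The reference class is partly decided by what happens after the index test.

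Section 5.1 defends the use of two reference standards on the ground that significant CHD is "likely to be detected equally well by both reference standards". That argument concerns whether a case is found. It does not cover whether a found case is graded critical or serious. Section 6.3 limits subgroup analyses to risk factors and timing of the test, so no planned analysis would show the effect.

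At stake is any accuracy figure reported for critical CHD alone, and any use of that figure in the economic model of section 6.5. The surgery and catheter wording, and the placing of late deaths, can also affect the combined class.

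**Working it through.** **The plan's own figures.** Section 6.1 assumes 75% sensitivity and says that 20,000 babies give 80% power to show sensitivity above 61% at 5 per 1000, and above 52% at 2 per 1000 (one-sided 2.5%, exact binomial limits). Exact enumeration gives 82.5% power at 61%, with 80% reached at 61.4%, and 80.8% at 52%. The figures reproduce, and the sample size is not in question here. There is no calculation for critical CHD alone.

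**Formula.** Let *s* be PO sensitivity, *f* the share of would-be critical cases with one of the six lesions, and *q1* and *q0* the proportions of PO-positive and PO-negative babies with those lesions who meet the 28-day rule. Then

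observed sensitivity = s[(1−f) + f·q1] / {s[(1−f) + f·q1] + (1−s)[(1−f) + f·q0]}.

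This takes *s* to be equal in both groups of lesions. It exceeds *s* if and only if q1 > q0. If *s* differs between the groups, losing cases also changes the lesion mix, and the condition is no longer exact.

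**Inputs.** s = 75% is from section 6.1. The documents give no value for *f*, *q1* or *q0*, so these are assumptions. With f = 0.5:

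| q1 | q0 | Calculation | Observed sensitivity |
|---|---|---|---|
| equal | equal | no change | 75.0% |
| 1 | 0.8 | 0.75 / (0.75 + 0.225) | 76.9% |
| 1 | 0.6 | 0.75 / (0.75 + 0.20) | 78.9% |
| 0.7 | 0.9 | 0.6375 / (0.6375 + 0.2375) | 72.9% |

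Over f = 0.3 to 0.7 these scenarios span 71.8% to 80.6%.

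**In whole babies.** As an illustrative count only, 20,000 × 2/1000 = 40 cases, of which 30 are detected: 75.0% (95% CI 58.8 to 87.3).

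- Moving 1, 2 or 3 false negatives to serious: 30/39 = 76.9%, 30/38 = 78.9%, 30/37 = 81.1%.
- Moving 1, 2 or 3 true positives to serious: 29/39 = 74.4%, 28/38 = 73.7%, 27/37 = 73.0%.

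**Combined class.** A baby who moves from critical to serious stays in both numerator and denominator, or in the denominator only, exactly as before. Combined sensitivity does not change.

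**Intervention wording.** Serious admits catheterisation or surgery. Critical admits death or surgery. A listed lesion treated only by catheter within 28 days is therefore not critical as worded. With no catheter item, the form cannot show that such a baby is serious either, and this reaches the combined class. A listed-lesion baby who dies after day 28 without intervention is not critical, and is serious only if requiring intervention is read as need.

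**The case against.** A reader might infer that critical-only sensitivity is inflated, and try to size it. Suppose 24 critical babies, half with a conditional lesion, and PO sensitivity of 90% and 60% in the two halves: (10.8 + 7.2)/24 = 75%. If 25%, 50% or 75% of the 4.8 missed conditional cases leave the class, sensitivity becomes 78.9%, 83.3% or 88.2%. The documents do not support that conclusion, because the calculation removes only false negatives. Section 1.1 says that death is more likely when collapse precedes diagnosis, and a missed baby who dies by day 28 remains a critical false negative. A detected baby first needing surgery after day 28 leaves as a true positive. With the same inputs, if 70% of detected and 90% of missed conditional cases meet the rule, the result is 15.84/21.36 = 74.2%. The sign is open.

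Other objections have force:

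- Appendix E says *requiring* surgery, which may mean need and not the operation date. This stands as to the text. The form, however, records only an actual date or that surgery is planned, so the date may decide in practice.
- The objectives already name critical and serious together, and equating life-threatening with critical is an inference. This also stands, so the point is confined to critical-only estimates unless section 2.1 is meant to make that class primary.
- Ignoring the date brings in stable babies with elective first-year repair. True: such an analysis differs in case mix as well as in bias.
- It would be too strong to say that catheter-only cases are lost. The form records lesion and diagnosis date, and sections 2.3 and 4.3.2 describe other sources. Only the item needed to grade them is absent.

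**Conclusion.** The point holds in limited form. For six lesions, critical status rests on an event that the unblinded PO result can influence, and the defence in section 5.1 does not address this. Critical-only sensitivity may be biased either way; the documents fix neither sign nor size. The illustration of about 2 points up per false negative moved, and 0.6 to 0.7 down per true positive moved, rests on an assumed class of 40 and the protocol's 75%. Movement between the two classes leaves the combined result unaffected.

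The wording gaps over catheterisation and late death do not depend on any assumption about direction, and they can affect the combined class. The documents do not show that the primary result is biased upward.

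**What to change.** 1. Keep critical and serious combined as the headline accuracy result, and reconcile the term life-threatening in section 2.1 with it.
2. Report critical-only sensitivity beside a pre-specified sensitivity analysis that counts every baby with one of the six lesions who dies, or has surgery or catheter intervention, within one year, whatever the date. State that this class includes elective repairs, so the two figures do not strictly bracket the truth.
3. Reconcile the intervention wording of critical and serious in Appendix E. State whether *requiring* means need or an actual date; that also settles where a listed-lesion death after day 28 without intervention belongs.
4. Add an item for catheter intervention, with its date, to the CHD case form.

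The cost is a wording change, one form item and one extra table. Surgery and death dates are already on the form; catheter dates are not and need the new item. The companion figure may be less favourable. Sample size, follow-up and care are unchanged.

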4.3.2 Congenital anomalies registry

At periodic intervals after recruitment, the regional congenital anomalies register (CAR) and mortality register will be queried using the diagnostic codes for cardiac abnormalities. Information retrieved will include the baby date of birth, location, date and nature of the diagnosis, any known outcome, including death and the baby's NHS number. We will also collect details on the diagnosis of Down's syndrome or any other congenital anomaly. Other identification details will be stripped to enable data transfer compliant with the Data Protection Acts. This will be sent to the Study Office to be cross-referenced with the babies already on the study database, matching for Baby and Mother NHS numbers and baby date of birth. For those that match, diagnostic information will be transferred to the study database for analysis. Unmatched babies will either have been missed at study hospitals, been born at non-participating hospitals within the region or have been born outside the region. These figures will help inform the study of completeness of verification. Additionally, registry holders in adjacent regions (e.g. Mersey and Trent) will be asked to be vigilant for notification of CHD cases from the West Midlands region.

A similar process will occur at the Birmingham Children's Hospital, which is the tertiary referral centre for the entire region. As the study progresses, if it appears that not all cases are being collected through either of these two methods, regional primary care trusts may be approached to search their databases using diagnostic READ codes. This will be substantially more labour intensive, so methods to maximise identification of CHD through the CAR and Children's Hospital sources will be explored first.

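### Appendix E counts catheterisation for Serious but not for Critical CHD, and the CHD case report form records surgery only, so severity class can depend on mode of treatment

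*Protocol*

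**What the plan says.** The accuracy objective (Protocol section 1.3) is critical and serious CHD, with a pointer to Appendix E for definitions. Section 2.1 describes the primary analysis as accuracy for life-threatening CHD, a term that Appendix E does not define.

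Appendix E sets the classes as follows.

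- **Critical, unconditional:** "All infants with hypoplastic left heart, pulmonary atresia with intact ventricular septum, simple transposition of the great arteries or interruption of the aortic arch".
- **Critical, conditional:** "all infants dying or requiring surgery within the first 28 days of life with the following conditions". Six lesions follow, beginning "coarctation of the aorta, aortic valve stenosis, pulmonary valve stenosis, tetralogy of Fallot", so both valve stenoses are among them.
- **Serious:** "Any cardiac lesion not defined as critical which requires intervention (cardiac catheterisation or surgery) within 1 year of age".
- **Significant** (outside the critical and serious target): "Any cardiac lesion which requires regular monitoring beyond 6 months or drug treatment but does not fall into serious or critical category".

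The CHD case report form in Appendix D asks "Has the baby had cardiac surgery? Yes No Planned", then the date if the answer is yes, and the type of surgery. It has no catheterisation item and no date for planned surgery. The main data collection form has no intervention item either. For the anomaly and mortality registers, section 4.3.2 says: "Information retrieved will include the baby date of birth, location, date and nature of the diagnosis, any known outcome, including death". It then says that a similar process will take place at the regional tertiary centre.

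**The concern.** There are two separate problems.

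First, the neighbouring rows of Appendix E use different triggers. Because the Serious row names catheterisation and surgery as distinct things, surgery in the Critical row cannot safely be read to include catheterisation. Two surviving babies with the same valve stenosis, both treated in the first 28 days, then fall into different classes according to how they were treated.

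Second, the form cannot apply the Serious definition in full. It collects one of the two qualifying interventions and omits the other. A form completed truthfully for a baby treated only by catheter says No to surgery. If nothing else is consulted, the Serious criterion looks unmet and Significant is the class that remains.

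At stake is which babies form the denominator of sensitivity. An analysis plan can settle how a definition is read, but it cannot recover an intervention or date that was never collected.

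**Working it through.** **1. Definitions applied to a survivor with a conditional lesion treated by catheter alone within 28 days**

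- Critical requires death or surgery within 28 days: not met on the literal wording.
- Serious requires that the lesion is not Critical and that it "requires intervention (cardiac catheterisation or surgery) within 1 year of age": met.
- Result: Serious. The baby is inside critical-plus-serious and outside critical-only.

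The four unconditional lesions stay Critical whatever the treatment. Deaths within 28 days from the six conditional lesions also stay Critical.

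**2. The form applied to any baby whose only first-year intervention was by catheter**

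- Surgery item: No. Date and type: blank.
- Serious cannot be confirmed from the form. The outcome then depends on other records or on staff writing the procedure under type of surgery.

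**3. The plan's own precision figures (section 6.1)**

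Inputs: N = 20,000, sensitivity 75%, one-sided 2.5%, exact binomial limits. Cases were taken as Binomial(N, prevalence) and detected cases as Binomial(cases, 0.75). Power is the probability that the exact lower limit exceeds the value to be ruled out, summed exactly.

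- Prevalence 5 per 1000: 20,000 × 0.005 = 100 expected cases. The value ruled out at 80% power is 61.4% (stated 61%).
- Prevalence 2 per 1000: 40 expected cases. The value ruled out is 52.4% (stated 52%).

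The stated figures reproduce and are not in dispute.

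**4. Illustrative effect on sensitivity**

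The documents give neither the catheter-only share f nor oximetry's sensitivity s in that group, so both are assumptions. With 75% in the remaining cases and every catheter-only case lost:

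true sensitivity = (1 − f) × 75% + f × s; recorded sensitivity = 75%.

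| f | s | True | Recorded minus true |
|---|---|---|---|
| 5% | 50% | 71.25 + 2.50 = 73.75% | +1.25 points |
| 5% | 30% | 71.25 + 1.50 = 72.75% | +2.25 points |
| 20% | 50% | 60 + 10 = 70% | +5 points |
| 20% | 30% | 60 + 6 = 66% | +9 points |

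For scale, the planned margin at 5 per 1000 is 75 − 61 = 14 points.

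If only half the catheter-only cases are lost in the last row, recorded sensitivity is (60 + 3)/0.9 = 70%. The overstatement is then 70 − 66 = 4 points.

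The sign depends on s. Fix overall true sensitivity at 75% and lose 10% of cases, so that recorded = (75% − 0.10 × s)/0.90:

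- s = 25%: 72.5/0.9 = 80.6%
- s = 50%: 70/0.9 = 77.8%
- s = 100%: 65/0.9 = 72.2%

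**5. Illustrative effect on power, N = 20,000, with 75% in the cases that remain**

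| Share of cases lost | 5 per 1000, against 61% | 2 per 1000, against 52% |
|---|---|---|
| 0% | 82% | 81% |
| 5% | 80% | 79% |
| 10% | 78% | 76% |
| 20% | 71% | 70% |

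**The case against.** The strongest reply is that classification does not rest on the form. No section makes it the sole classifying instrument, and Appendix E turns on what the lesion requires, not on a tick-box. Section 2.3 draws case identification up to one year from echocardiography, the anomaly register, the regional cardiology unit, the mortality survey, hospital information departments and, if necessary, primary care codes. The register list in section 4.3.2 is not worded as exhaustive, and section 6.5 expects one-year follow-up data on screen-positive babies. A planned operation could also be updated from these sources by one year.

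Much of this stands. It rules out two stronger inferences that a reader might draw:

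- **That the Appendix E mismatch itself removes babies from the primary denominator.** It does not. Under the combined target of section 1.3, the catheter-only neonate is Serious and stays in.
- **That catheter-only cases necessarily fall to Significant, with screen-positive ones scored as false positives.** This is a risk, not a certainty. Tertiary-centre records may supply the procedure, and screen-positive babies have the one-year follow-up as a further source.

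What the reply does not remove is the gap. Neither the register query nor the similar process at the tertiary centre is said to extract interventions, and the form has nowhere to put one. The screen-positive follow-up also cuts both ways: if it rescues only screen-positive babies, those lost are the missed cases, and recorded sensitivity rises.

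The difference between the two Appendix E rows may also be deliberate. The documents do not say, so the request should be to reconcile and state the rule, not to impose one.

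**Conclusion.** The inconsistency between the Critical and Serious rows is real, and the form does not capture the catheter criterion for Serious. The first problem affects only an analysis restricted to Critical CHD. That includes the life-threatening CHD analysis of section 2.1 if the term is taken to mean Critical, which the protocol does not spell out. The second puts catheter-only cases at risk of leaving the critical-plus-serious denominator unless another source supplies the intervention.

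The size and direction of any bias cannot be found from the documents. The overstatement of about 1 to 9 points assumes a 5–20% catheter-only share, total loss of those cases, and 30–50% sensitivity in them against 75% in the rest. Partial loss shrinks it, and better detection in these babies than in the rest reverses it. A reader might infer that the primary sensitivity will be inflated, but nothing in the protocol establishes how well oximetry detects these lesions. The point is of moderate importance and is not a must-fix.

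**What to change.** - **Appendix E:** reconcile the intervention wording of the Critical and Serious rows. The sponsor should decide and state whether catheter intervention counts for Critical.
- **CHD case report form:** replace the surgery item with intervention type (surgical, catheter or none), date of first intervention, and planned date where one is pending.
- **Completion:** fill in these fields for every CHD case found by any route, using the tertiary-centre records that section 4.3.2 already plans to query.

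The cost is one clarified definition, one revised form item and a few extra fields to abstract for about 100 cases (20,000 × 5 per 1000).
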